Household contact	A person who shared the same enclosed living space for one or more nights or for frequent or extended periods during the day with the index patient during the 3 months preceding TB screening
Suggestive of TB (radiological)	Chest X-ray findings interpreted by digital CXR with computer-aided detection (dCXR/CAD) and confirmed by a radiologist as consistent with TB.

Screening Definitions

Abbreviation	WHO- aligned terminology	W4SS	Molecular evidence of Mtb	dCXR/CAD
aTB-C	bacteriologically-confirmed asymptomatic TB	negative	Sputum Xpert positive, any grade OR Tongue swab [#] NAAT positive	any
sTB-C	bacteriologically-confirmed symptomatic TB	positive	Sputum Xpert positive, any grade OR Tongue swab [#] NAAT positive	any
aTB-U	bacteriologically-unconfirmed asymptomatic TB	negative	Sputum Xpert negative OR Tongue swab [#] NAAT negative	suggestive of TB*
sTB-U	bacteriologically-unconfirmed symptomatic TB	positive	Sputum Xpert negative OR Tongue swab [#] NAAT negative	suggestive of TB*
noTB	no evidence of TB	negative	negative	normal

* As interpreted by dCXR/CAD and confirmed by a radiologist

Tongue swabs will only be collected if approved by WHO and/or national authorities (South Africa or Indonesia) and in participants unable or refuse to produce sputum

Case Definitions

Abbreviation	WHO- aligned terminology	W4SS	Results of 3 sputum tests	dCXR/CAD	Other Clinical Data
aTB-C	bacteriologically-confirmed asymptomatic TB	Negative	1) Xpert >trace (1-3/3 sputum) OR 2) MGIT Mtb positive (1-3/3 sputum)	any	
sTB-C	bacteriologically-confirmed symptomatic TB	Positive	1) Xpert >trace (1-3/3 sputum) OR 2) MGIT Mtb positive (1-3/3 sputum)	any	
aTB-U	bacteriologically-unconfirmed asymptomatic TB	negative	1) 3/3 sputa Xpert Ultra negative AND 3/3 Mtb MGIT negative OR 2) 1-3/3 sputum Xpert Ultra trace AND 3/3 Mtb MGIT negative [#]	suggestive of TB *	clinical picture not explained by non-TB aetiology
sTB-U	bacteriologically-unconfirmed symptomatic TB	positive	1) 3/3 sputa Xpert Ultra negative AND 3/3 Mtb MGIT negative OR 2) 1-3/3 sputum Xpert Ultra trace AND 3/3 Mtb MGIT negative [#]	suggestive of TB *	clinical picture not explained by non-TB aetiology
noTB	no evidence of TB	negative	3/3 sputa negative by Xpert Ultra AND 3/3 MGIT Mtb negative [#]	normal*	

* As interpreted by dCXR/CAD and confirmed by a radiologist

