	
household contact IGRA positivity between aTB-C and sTB-C index cases is 0.90, 150 index cases of each TB phenotype in each setting will give us $\geq 80\%$ power to demonstrate that the transmission risk with aTB-C is not less than 50% of the transmission risk of sTB-C.
 
The index adults from the 600 households in each setting will be enrolled in the case-control phenotyping study. Assuming that the true sensitivity and specificity of the diagnostic tools are between 70-95%, with 150 aTB-C and 150 sTB-C cases, we will be able to estimate the sensitivity with a precision of $\pm 7.6\%$ to $\pm 4\%$. With 300 controls, we will be able to estimate the specificity with a precision of $\pm 5.3\%$ to $\pm 2.6\%$.
 
In each setting, after community screening, we expect to identify 500 participants with aTB-U who are eligible for the TB-U cohort. Based on the assumed annual progression rate, this sample size is expected to yield 31-66 individuals with progressive disease. With 50 individuals who progress and 100 who do not, we will have $\geq 80\%$ power to detect a difference of 0.50 standard deviations in mean biomarker concentrations between the two groups. If the prevalence of biomarkers in individuals who do not progress is 10-20%, we would have $\geq 80\%$ power to detect an increase to 30-40%.

Study Population	
Cross-sectional study of household Mtb infection (core study)
 
 • Community screening: Adolescents and adults (≥ 15 years) who reside in households with children 2-14 years and located within the study areas in each setting. • Child contacts: Children (2-14 years) who are household contacts of participants with aTB-C, sTB-C, or of randomly selected neighbourhood households with adults without TB 
Case-control phenotyping study (sub-study 1) Adolescents and adults (≥ 15 years) who were identified through community TB screening to have aTB-C, sTB-C and no TB
 
Cohort (sub-study 2) Adolescents and adults (≥ 15 years) who were identified through community TB screening with bacteriologically-unconfirmed TB (TB-U)

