2. OBJECTIVES

The **co-primary objectives** of the study are to compare Mtb infection, as defined by interferon release assay (IGRA) positivity, in child (2-14 years) household contacts of adults with bacteriologically-confirmed asymptomatic TB (aTB-C), with:

1. children in households with no adult with TB
2. children who are household contacts of adults with bacteriologically-confirmed symptomatic TB (sTB-C)

The **secondary objectives** are to:

1. Evaluate the diagnostic performance, feasibility, and acceptability of current tools for detecting aTB, including digital chest X-ray with computer-aided diagnosis (dCXR/CAD) and sputum Xpert, and sputum Mycobacteria Growth Indicator Tube (MGIT)
2. Evaluate the performance of novel diagnostic and screening tools to detect aTB including tongue swab NAAT, bioaerosol NAAT, exhaled breath condensate for lipoarabinomannan, cell free Mtb DNA and Mtb-specific T cell activation.
3. Characterize the features and longitudinal outcomes of sub-groups of people with aTB, including those with dCXR/CAD findings suggestive of TB but who are sputum Xpert & culture negative.

4. Establish a biobank and conduct studies of immune responses to understand the biology of aTB and define correlates of progression and resolution.
5. Model the contributions of aTB to global TB transmission and incidence and the potential impact of interventions to detect and treat this disease phenotype
6. Evaluate the proportion of child household contacts who convert from baseline negative to positive IGRA at 10-week visit or have a positive blood biomarker (including cell free DNA assay or positive Mtb-specific T cell activation assay).
7. Define the proportion of participants with TB screening results consistent with sTB-U who have a subsequent positive sputum Xpert, sputum MGIT, tongue swab NAAT or facemask NAAT.
8. Identification of transmission clusters using whole genome sequencing of Mtb strains obtained from participants with aTB-C, sTB-C and their household contacts.

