		
3. Participants selected as healthy controls
 
Inclusion criteria
 
 1. Adolescent/adult participant in TB screening 2. Screening W4SS negative 3. Screening sputum Xpert negative; AND Mtb MGIT negative* 4. Selected as a healthy control in the Cross-sectional study of Mtb infection in households (see above) 
ALL 3 groups above
 
Exclusion criteria
 
 1. Unable or unwilling to consent 
* MGIT results returning after enrolment may result in study group re-categorisation

Cohort study (sub-study 2)	Adolescents and adults (≥ 15 years) who participated in TB screening.	
Participants who meet the study case definition for bacteriologically-unconfirmed TB (TB-U)
 
Inclusion criteria:
 
 1. Adolescent/adult participant in TB screening 2. All three sputa Xpert are negative/ ‘trace’ AND all three sputum are Mtb MGIT negative 3. Screening dCXR/CAD interpretation is “suggestive of TB” 4. Clinical assessment at phenotyping visit does not suggest a non-TB aetiology for dCXR/CAD findings and is consistent with TB-U 5. Participant did not commence TB treatment after phenotyping visit 
Exclusion criteria
 
 1. Unable or unwilling to consent to longitudinal follow-up

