3.8 STUDY OUTCOMES/ ANALYSES

The study is designed to assess both the transmission of Mtb within households and the diagnostic performance of current and novel tools for detecting asymptomatic TB. The outcomes are grouped into primary and additional outcomes categories as outlined below.

CORE STUDY

Primary endpoint: Cumulative prevalence of child household contact IGRA positivity or confirmed TB (TB-C) at 10 weeks after diagnosis of the index case.

Additional outcomes/ analyses:

- (1) Proportion of children that convert from negative IGRA status at baseline to a positive IGRA status at 10-week visit.
- (2) Proportion of children with a positive plasma cell free Mtb DNA assay and positive Mtb-specific T cell activation assay, stratified by household group.
- (3) Whole genome sequencing of Mtb isolates from people with TB-C and household contacts.

CASE-CONTROL PHENOTYPING STUDY (SUB-STUDY 1)

- (4) Sensitivity, specificity, positive predictive value, negative predictive value, yield, feasibility, acceptability of digital chest x-ray with computer aided diagnosis (dCXR/CAD), sputum Nucleic Acid Amplification Test (NAAT), Mycobacteria Growth Indicator Tube (MGIT), tongue swab NAAT, and bioaerosol collection facemask mask NAAT to detect aTB-C.
- (5) Symptoms, health outcomes quality of life, comorbidities, nutritional status, and TB history, relative to group and W4SS status at screening.

(6) Proportion and characteristics of participants with detectable exhaled breath condensate lipoarabinomannan (LAM), positive plasma cell free Mtb DNA assay, positive Mtb-specific T cell activation assay and additional blood-based TB biomarkers, stratified by group.

TB UNCONFIRMED (TB-U) COHORT (SUB-STUDY 2)

(7) Time to event and factors associated with microbiological or clinical progression in participants with initially untreated aTB-U.

(8) Plasma biomarkers (including cell free Mtb DNA, Mtb-specific T cells, transcriptional signatures) that correlate with progression from aTB-U in the 12 months after TB screening

(9) Proportion and characteristics of participants with TB screening results suggestive of (TB-U) who have a subsequent positive sputum GeneXpert Ultra, sputum MGIT, tongue swab NAAT or Bioaerosol collection facemask mask NAAT.

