TB-UNCONFIRMED (TB-U) COHORT STUDY (SUB-STUDY 2)

A total of 1000 individuals (500 from Bandung and 500 from KwaZulu Natal) identified through the community-based screening who have chest x-rays suggestive of TB and negative baseline sputum will be followed prospectively. Based on published data that found that individuals with radiographic evidence of TB progressed to microbiologically-positive disease at an annualized rate of 10% (95% CI 6.2-13.3)⁶⁵, we anticipate 31-66 progressors to microbiologically-confirmed TB from each site.

With 50 individuals who progress and 100 who do not, we will have $\geq 80\%$ power to detect a difference of 0.50 standard deviations in mean biomarker concentrations between the two groups. If the prevalence of biomarkers in individuals who do not progress is 10-20%, we would have $\geq 80\%$ power to detect an increase to 30-40%.

STAGE GATE

We have used our best estimates of the prevalence of TB-C, prevalence of IGRA positivity, number of children per household, and value of the ICC to inform our sample size calculations, based on the available data in each setting. However, given the limited data available, there is uncertainty in these assumptions and a small change in any one of these (e.g. in household size, ICC, or the prevalence of

IGRA positivity) can have a large impact on our power. Therefore, after 20% of the population has been screened at each site (12,000 in Bandung and 6000 in KwaZulu Natal), we will assess the accuracy of the key assumptions used in our sample size calculations. Specifically, we will analyse the available data to determine the population prevalence of aTB-C, the proportion of children aged 2-14 years who are IGRA positive, average household size, and the estimated ICC. We will then use these revised estimates to further refine our power calculations for the co-primary endpoints. The results will be discussed with the funders and, if necessary, we may adjust the project sample size, budget and timelines to ensure sufficient power to address both co-primary endpoints. We will also evaluate any data available for the TB-U cohort (proportion of participants meeting the screening definition of TB-U who are confirmed aTB-C by 2 additional sputum specimens, proportion of TB-U participants who progress to TB-C) and we may adjust the TB-U cohort size to address its powering endpoint.

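### The protocol contradicts itself on whether the TB-U cohort's 500 per site and its 31-66 progressors count aTB-U only or all TB-U

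*Protocol*

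**What the plan says.** **Who may enter.** Section 3.3, Table 1, opens the cohort to "Participants who meet the study case definition for bacteriologically-unconfirmed TB (TB-U"). None of the five inclusion criteria mentions W4SS. The case-definition table lists "bacteriologically-unconfirmed symptomatic TB" (sTB-U) beside its asymptomatic counterpart, so both belong to TB-U. The one filter bearing on sTB-U is criterion 5: "Participant did not commence TB treatment after phenotyping visit". By contrast, all three sub-study 1 groups in the same table carry an explicit W4SS criterion.

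**Whom the 500 and the 31-66 count.**
- Protocol Summary, Sample size: in each setting, "we expect to identify 500 participants with aTB-U who are eligible for the TB-U cohort". The 31-66 progressors are derived from that number.
- Section 5.1: "A total of 1000 individuals (500 from Bandung and 500 from KwaZulu Natal") "who have chest x-rays suggestive of TB and negative baseline sputum will be followed prospectively". No symptom condition is given, and the same 31-66 per site is derived.

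**What the outcomes concern.** Outcome 7 in section 3.8 covers "factors associated with microbiological or clinical progression in participants with initially untreated aTB-U". Outcome 8 (plasma biomarkers) is also limited to progression from aTB-U. Outcome 9 is for TB-U. The analysis in section 5.2 counts person-time from entry to the TB-U cohort and does not restrict to aTB-U.

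**Objective 7.** The Summary states it for TB-U. Section 2 reads "Define the proportion of participants with TB screening results consistent with sTB-U who have a subsequent positive sputum Xpert".

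**The concern.** Three statements that should name one population name two. Eligibility and section 5.1 describe a cohort of any symptom status. The Summary's target and outcomes 7 and 8 describe an asymptomatic one. No text caps sTB-U entry, gives its expected share, or says whether sTB-U participants use up the 500 places.

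If 500 TB-U are enrolled and outcomes 7 and 8 are analysed as worded, the aTB-U progressors number fewer than the Summary states whenever any sTB-U participant enters. If everyone is analysed, as section 5.2 implies, the results describe a mixed group and not the aTB-U question that outcomes 7 and 8 pose. Section 5.2 analyses each setting separately, so pooling the two sites does not absorb a shortfall.

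A later analysis plan can choose an analysis set. It cannot add aTB-U participants who were never enrolled.

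**Working it through.** **Inputs from the documents**
- 500 per site (Summary; section 5.1).
- Annual progression 10%, 95% CI 6.2-13.3%, for people with radiographic evidence of TB (section 5.1).
- 50 progressors against 100 non-progressors, difference 0.50 SD, at least 80% power (Summary; section 5.1).

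**Assumptions, because the documents are silent**
- sTB-U share of the cohort, s: 10%, 20%, 30% and 50%.
- The same progression rate in aTB-U and sTB-U.
- Two-sided 5% test.
- No loss to follow-up, as in the plan's own product.

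**Step 1: reproduce the plan.** Progressors = 500 × annual rate.
- 500 × 0.062 = 31.0
- 500 × 0.10 = 50.0
- 500 × 0.133 = 66.5

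This matches 31-66. Two-sample t-test power for 50 against 100 at 0.50 SD is 81.8% (normal approximation 82.3%), which agrees with the stated 80% or more. The 50 in the power statement equals the expected count at the central rate, so there is no reserve.

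**Step 2: count aTB-U only.** aTB-U progressors = 500 × (1 − s) × rate. Power is the two-sample t-test at 0.50 SD, using the count at the 10% rate. The last column takes every aTB-U non-progressor as comparator: 450, 405, 360, 315 and 225 people.

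| s | aTB-U enrolled | Progressors at 6.2% / 10% / 13.3% | Power vs 100 non-progressors | Power vs all aTB-U non-progressors |
|---|---|---|---|---|
| 0 | 500 | 31.0 / 50 / 66.5 | 81.8% | 91.7% |
| 10% | 450 | 27.9 / 45 / 59.9 | 79.0% | 88.8% |
| 20% | 400 | 24.8 / 40 / 53.2 | 75.6% | 84.9% |
| 30% | 350 | 21.7 / 35 / 46.6 | 71.5% | 79.9% |
| 50% | 250 | 15.5 / 25 / 33.3 | 60.2% | 65.6% |

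The normal approximation gives values up to about one percentage point higher (72.1% at s = 30% against 100).

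**Step 3: enrolment needed to keep 500 aTB-U.** Total TB-U = 500 / (1 − s), rounded up: 556, 625, 715 and 1,000 per site for s of 10%, 20%, 30% and 50%.

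**The case against.** The strongest reply is that section 5.1, the formal sample-size section, is consistent with Table 1. It counts TB-U, takes a rate for radiographic TB that is not specific to asymptomatic people, and obtains 31-66 for that group. On that reading the stated number is met, and the Summary's aTB-U is a slip in one sentence. This stands as far as it goes. A reader might infer that the whole target is for aTB-U and that the plan will therefore miss its progressor count. The documents do not support that, because section 5.1 says otherwise. But outcomes 7 and 8 also name aTB-U, so correcting the Summary alone would leave 31-66 describing a population that those outcomes do not.

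A cohort wider than some of its outcomes is not an error in itself. Outcome 9, and objective 7 as the Summary words it, use all TB-U, and restricting an analysis by recorded W4SS status is ordinary analysis-plan content. That is fair. What it cannot settle is who counts towards the 500.

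A reader might also infer that sites will close at 500 consecutive TB-U participants. No such rule is written, and the Summary's sentence is an expected yield. The shortfall is conditional on enrolment being counted as section 5.1 describes.

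A larger power loss, to about 73%, 67% and 52% at shares of 20%, 30% and 50%, appears only if the non-progressor group is shrunk to keep a 1:2 ratio. Nothing requires this, since well over 100 aTB-U non-progressors would remain in follow-up at each share.

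Finally, the stage gate in section 5.1 allows the cohort to be resized. That is a real safeguard, but it looks at the proportion of TB-U participants who progress, so as written it would not show a shortfall in aTB-U.

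**Conclusion.** The contradiction is established from the text alone and depends on no assumption: the Summary counts aTB-U, Table 1 and section 5.1 count TB-U, and outcomes 7 and 8 concern aTB-U. The mismatch in objective 7 is equally plain, though it has no bearing on progressor numbers or power.

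The size of the consequence cannot be fixed from the protocol. The sTB-U share is not given and may be small, because those who start treatment do not enter. Against the stated 100 comparators, power for 0.50 SD falls just below 80% at a share of about 10%. With all aTB-U non-progressors it stays at about 80% up to a share of about 30%. These figures rest on an equal progression rate in both groups. At the same overall rate, faster progression in sTB-U would lower the aTB-U count further, and slower progression would raise it.

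This should be corrected before enrolment is counted. It affects a stated figure and the filling of the cohort, not the validity of the core study.

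**What to change.** Name one population for the 500 per site, the 31-66 progressors and outcomes 7 and 8. Either of two routes is consistent:

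1. **aTB-U target.** State in Table 1 and section 5.1 that only participants with a negative screening W4SS count towards the 500. Follow sTB-U as an additional, separately reported stratum.
2. **TB-U target.** Restate the Summary and outcomes 7 and 8 as TB-U, stratify the analysis by screening W4SS, and give the expected number of aTB-U progressors with its power and the comparator group used.

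Under either route, have the stage gate report progression by W4SS status, and word objective 7 identically in the Summary and section 2.

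The cost is protocol wording and a W4SS counter at enrolment. W4SS is already recorded at Visit 1. Under route 1, total follow-up grows with the sTB-U share if all of them are followed: 625 per site at an assumed 20%. Under route 2, the stated number of aTB-U progressors may be less favourable than 31-66.

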[#] If one of the three collected MGIT cultures is contaminated rather than negative, this will be considered acceptable, provided that the remaining two MGIT cultures are negative and all three sputum Xpert results are also negative

PROTOCOL SUMMARY

Title	Asymptomatic Tuberculosis Transmission in Indonesia and South Africa
Short Title	ATTIS Study
Protocol number	A-ATTIS-001
Settings	Contiguous geographical areas (study areas) in King Cetshwayo and uMkhanyakude Districts, KwaZulu-Natal, South Africa and Bandung City, Indonesia
Study Duration	30 months
Summary of Approach	
This is a cross-sectional study comparing the Mtb infection status in child household contacts of people with asymptomatic TB, people with symptomatic TB and community controls (core study). These households will be identified through community-based TB screening.
 
A case-control phenotyping study (sub-study 1) will be conducted on participants classified as aTB-C, sTB-C and noTB and will include additional diagnostic tests, clinical phenotyping and biobanking.
 
A TB-Unconfirmed cohort (sub-study 2) study will be conducted on participants with bacteriologically-unconfirmed TB (TB-U) that does not meet criteria for TB treatment and will include serial clinical evaluation, diagnostic testing and biobanking.
 
A mathematical modelling study (sub-study 3) will utilise empiric data from the study to estimate the contribution of asymptomatic TB to local and global TB transmission and incidence and the impact of potential interventions.

Co-primary Objectives	Compare Mtb infection, as defined by interferon release assay (IGRA) positivity, in child household contacts (2 to 14 years) of adults with bacteriologically-confirmed asymptomatic TB (aTB-C), with: 
 (1) children in households with no adult with TB (2) children who are household contacts of adults with bacteriologically-confirmed symptomatic TB (sTB-C).
Secondary Objectives	
 (1) Evaluate the diagnostic performance, feasibility and acceptability of current diagnostic tools to detect aTB, including digital chest x-ray with computer aided diagnosis (dCXR/CAD), sputum Xpert, and sputum Mycobacteria Growth Indicator Tube (MGIT). (2) Evaluate the performance of novel diagnostic and screening tools to detect aTB including tongue swab NAAT, bioaerosol NAAT, exhaled breath

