Case-control phenotyping study (sub-study 1) AND Cohort study (sub-study 2)	
Visit 1.1 Facility based clinical assessment (weeks 1-8)
 
 • Individual consent/ assent • Referral to research clinic for phenotyping 
 ◦ Blinded structured questionnaire, include symptoms, quality of life, health outcomes ◦ Physical examination ◦ Collection of 2 sputum samples (Xpert, MGIT culture)* ◦ Collection of samples for novel diagnostic tests 
 ▪ Tongue swabs ▪ Facemask ▪ Exhaled breath condensate ▪ Venous blood – HIV; VL; HbA1C; FBC/smear; Mtb cell free DNA; Mtb-specific T cell activation, biobanking specimens ◦ Physician review of participant's TB screening results • Clinical referral for TB and non-TB care • Telephonic review of linkage to care and well-being • Electronic / physical record review to confirm TB treatment initiation and completion
TB-U Cohort study (sub-study 2)	
Visit 1.2, to 1.5: Longitudinal follow-up (Months 3, 6, 9 & 12)
 
 • Clinical assessment including symptoms, quality of life, health outcomes • Physical examination • Sputum samples x 2 (Xpert, MGIT culture) • Venous blood – Mtb cell free DNA; Mtb-specific T cell activation, biobanking specimens • Digital chest x-ray • Facemask and Exhaled Breath Condensate, in a subset of participants • Physician review • Clinical referral for TB or non-TB care

Tongue swabs will only be collected if approved by WHO and/or national authorities (South Africa or Indonesia) and in participants unable or refuse to produce sputum

* If eligibility is based on a positive tongue swab collected due to unsuccessful sputum collection at visit 1.0, three sputum samples will be collected at visit 1.1

[figure not shown]
\$ HIV testing in children will only be performed in South Africa

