A community, or clinic-based follow-up visit or telephonic contact will be conducted between weeks 2 and 14 (**Visit 2.3**) for participants with positive results. This visit will be used to provide IGRA and sputum results (where sputum was collected) and to confirm that appropriate referral to the local health clinic for TPT initiation or TB treatment, as indicated, has occurred. The study team will provide support to strengthen local health care facilities by building capacity in the provision of TPT for household contacts of participants diagnosed with TB, in accordance with national guidelines.

In South Africa, HIV results will be provided with post-test counselling using language appropriate to the child's age and maturity. Children aged 12–14 years may receive their results without a parent or guardian present but will be encouraged to involve their parent or guardian in the discussion and ongoing support.

Participants with negative results will be contacted via telephone or SMS. This visit will mark the End-of-Study visit for household contacts.

SUB-STUDIES 1 and 2

Within two weeks of TB screening, eligible participants will be invited to attend the research clinic for **Visit 1.1**. Participants will remain blinded to their screening results at the time of the visit. At Visit 1.1,

individual consent or assent will be obtained for participation in the sub-studies. This visit will include all participants being enrolled in either Sub-study 1 (aTB-C, sTB-C, and control participants) or Sub-study 2 (TB-U participants).

At the clinic, a **blinded structured questionnaire** will be administered to collect detailed information on symptoms, quality of life, functional status, and health outcomes. This will be followed by a comprehensive physical examination, including assessment of vital signs, height, weight, lymphadenopathy, and breath sounds. Two samples, either an early-morning and spot specimen or two spot specimens, as per site procedures will be collected for Xpert and MGIT culture testing. Participants whose screening molecular test was a positive tongue swab NAAT, will have 3 sputum specimens collected.

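### Where tongue swabs are used, a swab-negative person screened as TB-U gives only two sputa, but entry to the TB-U cohort requires three

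*Protocol*

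**What the plan says.** **Screening.** A participant who cannot or will not give sputum has a tongue swab instead, provided swabs are approved (Protocol 3.5). In the Screening Definitions table, the molecular condition for TB-U begins "Sputum Xpert negative OR Tongue swab", so a negative swab with a suggestive X-ray is enough. The list of screening groups in 3.5 repeats this and gives noTB the same swab-negative alternative.

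**Visit 1.1.** Two sputa are the default. Section 3.5 makes one exception: "Participants whose screening molecular test was a positive tongue swab NAAT, will have 3 sputum specimens collected". The footnote to Table 2 (3.4) has the same restriction: "If eligibility is based on a positive tongue swab collected due to unsuccessful sputum collection at visit 1.0, three sputum samples will be collected".

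**Cohort entry.** The Table 1 cell opens with "Participants who meet the study case definition for bacteriologically-unconfirmed TB (TB-U". Criterion 2 then asks for three sputa, each Xpert negative or trace, "AND all three sputum are Mtb MGIT negative". The first route of the TB-U case definition is "3/3 sputa Xpert Ultra negative AND 3/3 Mtb MGIT negative"; the second allows trace results, again with three negative cultures.

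**Contamination.** Footnote # to the Case Definitions reads "If one of the three collected MGIT cultures is contaminated rather than negative, this will be considered acceptable". The allowance is conditional: both other cultures must be negative, and so must every one of the Xpert results.

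**Controls.** Section 3.5 draws controls at random from noTB participants in the neighbourhood. Table 1 requires a sub-study 1 control to be negative on both Xpert and MGIT of the screening sputum, and the noTB case definition needs three negative sputa.

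**The concern.** The protocol recognises that a person screened by swab lacks the first of the three sputa, and it supplies the missing one only when the swab is positive. A negative swab with a suggestive X-ray leads to the cohort, where three sputa are equally required, and no section supplies the third.

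The loss would be selective. Everyone on this route failed to produce, or refused, a screening sputum, so the TB-U cohort would consist only of people who gave sputum at screening or had a positive swab. The people affected would first go through visit 1.1, with 40 mL of blood and the novel tests, before being found unable to meet the definition.

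For controls, the protocol summary says that the index adults of all 600 households per setting enter sub-study 1. A control chosen on a swab alone cannot do so under the Table 1 criterion.

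**Working it through.** **1. The plan's own cohort figure.** Section 5.1 expects 31 to 66 progressors per site among 500 people, from an annualised rate of 10% (95% CI 6.2 to 13.3). 500 × 0.062 = 31.0 and 500 × 0.133 = 66.5, so the figure reproduces. It is not in dispute; it presumes 500 people who meet the entry rule.

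**2. Sputa available when the case definition is confirmed.** Section 3.5 confirms it once visit 1.1 cultures are final.

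| Screening route | Screening sputa | Visit 1.1 sputa | Total | Required |
|---|---|---|---|---|
| Sputum given | 1 | 2 | 3 | 3 |
| No sputum, swab positive | 0 | 3 | 3 | 3 |
| No sputum, swab negative | 0 | 2 | 2 | 3 |

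The stage-gate text in 5.1 also speaks of two additional sputa for people who meet the screening definition of TB-U, which agrees with the first row. The third row cannot reach three whatever the results.

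**3. Size of the swab-negative group.** The protocol gives no sputum failure rate. If a share t of otherwise eligible screenees were on this route, the number per 500 would be 500t. For assumed t = 5%, 10% and 20% that is 25, 50 and 100. Where swabs are not approved it is 0.

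**4. Controls.** Selection pool (3.5): W4SS negative, Xpert or swab negative, normal X-ray. Sub-study 1 criterion (Table 1): screening sputum Xpert negative and MGIT negative. A swab-only person satisfies the first and has no screening sputum for the second. With two sputa at visit 1.1, the 3/3 noTB definition is also out of reach.

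**5. Contamination (illustration only).** The protocol gives no contamination rate. With an assumed rate c per culture, independent between cultures, the probability that exactly one of three is contaminated is 3c(1−c)²:

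- c = 3%: 3 × 0.03 × 0.97² = 0.085, about 42 of 500
- c = 5%: 3 × 0.05 × 0.95² = 0.135, about 68 of 500
- c = 10%: 3 × 0.10 × 0.90² = 0.243, about 122 of 500

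These are upper bounds for the number on whom criterion 2 (read literally) and footnote # differ. They include people with a trace result, whom neither text admits when a culture is contaminated.

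**6. Where the footnote is marked.** In the TB-U rows the # stands after the second route, the one for trace results, while its condition requires all three Xpert results to be negative. The table treats negative and trace as separate routes, so on a literal reading the allowance cannot operate on the route where it is marked. If the mark is meant for the whole cell, it serves the first route only.

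**The case against.** **The swab route may never be used.** Swabs depend on approval, and the background section says WHO has not yet issued a recommendation. This stands: the group may be empty, and the finding is conditional.

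**Screening and case definitions are separate stages.** Someone with two sputa is a screenee who fails the case definition, and attrition after visit 1.1 is expected anyway through confirmed TB, a non-TB cause or treatment. It is right that these people are TB-U only by the screening definition. But the other losses follow from clinical findings, whereas this one follows from a specimen that the schedule never asks for.

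**Criterion 2 is shorthand.** The line above it invokes the case definition, and with it footnote #. This largely stands. A reader might infer that people with one contaminated culture are shut out, or that the two countries would build different cohorts. The documents do not support either as a firm conclusion: the same cell imports the footnote, and the study team confirms case definitions. Nor is a trace result with one contaminated culture a conflict over admission, since neither text admits it; what is unclear is the placement of the footnote.

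**Difficult cases go to the Clinical Safety Committee (8.3).** That committee can advise on categorisation, but nothing in its remit changes an inclusion criterion or supplies a missing sputum.

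**The control criterion may simply narrow the pool.** That is possible, but selection in 3.5 comes first and does not exclude swab-only participants. A reader might also infer damage to the co-primary comparison with control households. The documents do not show that: under Table 1 a child qualifies through an adult selected as a control, whether or not that adult enters sub-study 1.

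**Conclusion.** The point holds in a narrow form. Where tongue swabs are approved, everyone who gives no screening sputum, has a negative swab and has a suggestive X-ray is screened as TB-U and then cannot enter the cohort, because two sputa are scheduled and three are required. This follows from the text without any assumption. The number affected cannot be derived; the range of 0 to 100 per 500 in the working rests on assumed shares of up to 20%. The mismatch between control selection and the sub-study 1 control criterion is equally textual and has the same condition.

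The contamination allowance is a secondary inconsistency of wording. Its effect depends on which line staff follow, and the figures of 42, 68 and 122 per 500 are illustrative upper bounds under assumed, independent contamination rates.

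**What to change.** Reconcile the Screening and Case Definitions with footnote #, Table 1 (3.3), the Table 2 footnote (3.4) and section 3.5:

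1. Extend the existing three-sputum rule at visit 1.1 to every participant without a screening sputum, whatever the swab result. Alternatively, define TB-U and noTB on the sputa obtained, with a stated minimum.
2. Make cohort criterion 2 refer to the case definition including footnote #, and state whether the footnote applies to trace results.
3. Align the sub-study 1 control criterion with the selection route in 3.5, either by admitting swab-screened controls on stated terms or by barring them from selection.

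The cost is protocol wording plus, under the first option in item 1, one more sputum at an existing visit for a subset. Some people who gave none at screening may fail again, so that option may not recover everyone. Defining the groups on the sputa obtained needs no extra specimen but excludes confirmed TB a little less strictly in people with two sputa. The change should be made before swabs come into use, because sputa not collected at visit 1.1 cannot be recovered later.
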